Date: May 28, 2020
Principal Investigator: [name]
Application Number: IRB00159636

**Assessing the Safety of Buprenorphine in People With Sickle Cell Disease
NCT03492099
Last updated on: May 28, 2020**

JHM IRB - eForm A – Protocol

- Use the section headings to write the JHM IRB eForm A, inserting the appropriate material in each. If a section is not applicable, leave heading in and insert N/A.
- When submitting JHM IRB eForm A (new or revised), enter the date submitted to the field at the top of JHM IRB eForm A.

1. Abstract

Provide no more than a one page research abstract briefly stating the problem, the research hypothesis, and the importance of the research.

There are only a few therapies available to decrease vaso-occlusive crisis (VOC) in people with sickle cell disease; stem cell transplant, chronic transfusion therapy and hydroxyurea. Most recently L-glutamine has been FDA approved but it is reserved for only a small subset of people with the disease. Transplant is the only known cure for this disease. Its safety and efficacy, especially in adults, remains a concern and is only available to adults as a research protocol. Chronic transfusion therapy is an effective way of decreasing the risk of several complications of SCD including stroke and VOC events. Hydroxyurea is an effective disease-modifying therapy that decreases the risk of VOC by 50%. However, neither chronic transfusions nor hydroxyurea have been shown to decrease the intensity of chronic pain. There is a subset of patients who are on effective disease modifying therapy, yet continue to have frequent acute visits for parenteral opioids and are maintained on high dose oral opioids as outpatients.

Buprenorphine is a partial mu-agonist and kappa antagonist and has a very high affinity for the mu receptors, with an elimination half-life of 28-37 hours for the sublingual administration. The lower risk for misuse, diminished withdrawal symptoms and cravings for opioids as well as the reduced risk of overdose in this drug make it an appealing alternative to full agonist opioid use in a subset of patients with sickle cell disease on who are unable to wean off of opioids.

Most relevant to SCD patients on high doses of opioids, there has been recent data on successful conversion for patients with chronic pain who are on high-dose opioids, from 100mg to 400mg morphine equivalents, to SL buprenorphine. This study reported a decrease in pain scores after the initiation of SL buprenorphine therapy for more than two months. Our goals of this study is to assess patient important outcomes post conversion to buprenorphine.

2. Objectives

The purpose of this study is to assess the safety and benefit of converting adults with sickle cell disease on high dose opioid therapy with evidence of opioid use disorder to buprenorphine. The primary outcome will be to assess the safety of the protocol. Secondary outcomes will include measures of acute care utilization and health related quality of life after conversion.

Primary Endpoint: This will be a descriptive study assessing the safety and benefit of converting subjects from full agonist opioids to buprenorphine. Data will be collected on need for hospitalization within 72 hours of conversion due to withdrawal induced VOC, as well as average COWS scores.

Secondary Endpoint: Measurement of quality of life, decrease in pain measured by the BPI and Promis pain tools decrease acute care utilization. In addition we will collect data from the 15-20 patients that have

already been converted to buprenorphine as part of routine care to formally examine utilization pre and post conversion.

3. Background

Sickle cell disease (SCD) is a genetic disorder of the hemoglobin that leads to severe morbidity and early mortality. It is the most common disease detected by newborn screening efforts in the United States (U.S.) [1]. Between 80,000 and 100,000 individuals in the U.S. are affected by some form of SCD [2]. African-Americans (AA) are most affected in the U.S., as 1 per every 400 AA newborns is born with the disease. There are several genotypes that lead to similar phenotypes in SCD. Those who are homozygote for the sickle mutation (SS) have the most severe form of the disease and typically make up 60-70% of those with sickle cell disease. People with SC disease are compound heterozygotes and are considered to have a milder phenotype but there is a wide spectrum and chronic pain is quite prevalent in people with SC disease often due to avascular necrosis of the hips and shoulders. The damage SCD inflicts on sufferers is dramatic. The disease reduces life expectancy by approximately 30 years compared to the general population [3]. Furthermore, the disease limits quality of life - as severely as does end-stage renal disease requiring hemodialysis [4].

The best-known complication of SCD is the vaso-occlusive crisis (VOC). These acute, excruciatingly painful events are the leading cause of hospital and emergency department utilization [5], and can be associated with such lethal and disabling complications as acute chest syndrome and stroke. Triggers for the development of VOC include intravascular volume depletion, stress and infection. In addition to these acute episodes of pain, the prevalence of chronic pain is very high [6], [7]. Acute and chronic pain and disease severity contribute to extraordinarily high levels of unemployment, and decreased productivity in this patient population. Therefore, the persistent balance of pain control and quality of life remains a challenge.

The mechanisms of chronic pain in SCD are poorly understood. A number of factors ranging from genetic to behavioral likely regulate the pain response in people with SCD and include interactions between the nervous, endocrine, and immune systems [8]. The role of the immune system is of particular interest in understanding pain due to SCD; the role of inflammation in acute painful episodes is currently being explored through clinical trials investigating new treatment modalities. That ongoing inflammation may play a role in chronic pain is suggested by the identification of elevated levels of inflammatory cytokines and substance P, the neuropeptide modulator of inflammation and nociception, in SCD [9]. Additionally, chronic pain resulting from SCD is now hypothesized to be partly a disorder of central sensitization and peripheral neural sensitization. Central sensitization is a complex phenomenon, with contributions from plasticity induced by excitatory amino acids via NMDA receptors [10] and neural changes induced by inflammatory mediators and other nociceptive chemical messengers. To make things more complicated, our group and others have shown that opioid induced hyperalgesia may contribute to chronic pain via central sensitization [11]. A fascinating outcome of successful, curative stem cell transplant is that almost every adult patient reported in the literature who was on chronic opioid therapy prior to transplant was weaned off of those medications post-transplant. This phenomenon, which we have seen in our own transplant population, suggests that bone damage is likely a small component of the chronic pain and raises even more concern that hyperalgesia induced by opioid use itself may be playing a role in the patient experience of chronic pain.

The current standard of care for the treatment of chronic pain in people with sickle cell disease is the use of both long and short acting opiates. Full agonists are opioid drugs that bind completely to mu opioid receptors in the brain, and cause them to produce endorphins which relieve pain [12]. The best approach to the treatment of chronic pain in people with sickle cell disease is unclear and there is little literature on the effectiveness of chronic opioid therapy in this patient population. In a recently published paper we compared pain symptoms in 83 adults who were either on chronic opioid therapy or not. We found that those on chronic opioid therapy exhibited greater levels of clinical pain, central sensitization as well as higher levels of healthcare utilization. This suggested that despite the use of opioid therapy, patients continued to have a very high symptom burden.

As with any persistent use of opiates for other chronic pain conditions, there is an increase probability of opioid dependency and in rare cases, an increased probability of aberrant opioid use. Opioid induced hyperalgesia, central sensitization and refractory pain are potential long-term outcomes for many SCD patients on long term opioids, potentially leading to higher doses of opioids over time [11]. Therefore, there may be great value in reducing the use of full agonist opioids for patients with sickle cell disease.

There are only three therapies available to decrease vaso-occlusive crisis (VOC); stem cell transplant, chronic transfusion therapy and hydroxyurea. Transplant is the only known cure for this disease; its safety and efficacy, especially in adults, remains a concern and is only available to adults as a research protocol. Chronic transfusion therapy is an effective way of decreasing the risk of several complications of SCD including stroke and VOC events [13]. Hydroxyurea is an effective disease-modifying therapy that decreases the risk of VOC by 50%. However, neither chronic transfusions nor hydroxyurea have been shown to decrease the prevalence of chronic pain. There is a subset of patients who are on effective disease modifying therapy, yet continue to have frequent acute visits for parenteral opioids and are maintained on high dose oral opioids as outpatients.

Prior to enrolling on this trial participants will have already made a decision to convert to buprenorphine therapy after lengthy discussions with the clinical care team. That discussion includes risks and benefits of buprenorphine and the need to be in mild- moderate withdrawal prior to initiating buprenorphine. In addition, most patients will be weaned down as much as possible from their current opioid dose prior to initiating the protocol below.

- a. Study design, including the sequence and timing of study procedures.
 1. **Within 90 days prior to day 0** subject will sign Informed Consent Form (ICF) (R) , have urine toxicology testing, and complete HRQoL tool (ASCQ-Me) (R),brief pain inventory (BPI) (R), the PROMIS Pain Interference – Short Form instrument (R), and the PROMIS Physical Function – Short Form instrument (R). The ASCQ-Me tool is a validated health related quality tool for use specifically in SCD. The PROMIS Pain Interference instrument measures the degree to which pain hinders social engagement and life enjoyment. The PROMIS Physical Function instrument measures the degree to which pain affects everyday physical activities.
 2. Data will be collected on acute care utilization, sickle cell disease co-morbidities from chart abstraction and recorded in case report forms.
 3. **Day 0:**
 - a. Subject will complete ASCQ-Me, PROMIS Pain Interference, PROMIS Physical Function, and BPI with 7 day anchor (R).
 - b. Prior to discharge from SCIC subject will have COWS assessment, pain rating collected.
 4. **Day 1:** Subject will return to repeat COWS.
 5. Subject will return **day 14, day 30, day 90, and day 180** to repeat ASCQ-Me, PROMIS Pain Interference, PROMIS Physical Function, and BPI (R), or subject will complete these surveys over the phone or online on those days in lieu of coming for a study visit. Acute care utilization will be collected from subject, medical record and Crisp.

- a. The only change in the ICF version approved by IRB on November 6 2019 was the option of completing the study surveys remotely (over the phone or online) for participants. Patients that were consented using a previous version of the ICF and are enrolled to the study before the November version, have agreed to all study procedures, but have not agreed to having the option to complete the study surveys online or over the phone. The study team will reach out to these **currently enrolled patients** during in-person clinical visits, via telemedicine appointments or over the phone to re-consent them to the study in-person or remotely using the ICF version approved on November 6 2019. On the instances when the re-consent process is done remotely, the person obtaining the re-consent will:
 - i. Sign, print their name, and add date and time of the re-consent, under the consent line.
 - ii. Add on the line of the patient signature: *[First and Last name of patient]* provided verbal affirmation of this newer version of their previously signed consent (the only change from previous signed version by patient is that the surveys can be completed remotely).
- 6. Data will be extracted from EPIC and CRISP on health care utilization for the 6 months prior to enrollment and 3 years post conversion.
- 7. We will also collect data on the 15-20 patients that we have now converted to buprenorphine. We will retrospectively review charts to collect genotype data, acute care utilization (ED, sickle infusion clinic and hospitalizations), COWS scores, sex, age and any complications that occurred with conversion. These subjects will be asked to complete ASCQ-Me and Promis tools.
- b. (distinguish research procedures from those that are part of routine care).
All research activities are noted with (R) above.
- c. Study duration and number of study visits required of research participants.
Each participant will be enrolled for 3 years and will have up to 6 study visits with the possibility of completing the ASCQ-Me, BPI and Promis tools over the phone or online instead of coming in for a study visit. The initial visit is part of routine care that we provide for conversion from opioids to buprenorphine.
- d. Blinding, including justification for blinding or not blinding the trial, if applicable. NA
- e. Justification of why participants will not receive routine care or will have current therapy stopped.
NA
- f. Justification for inclusion of a placebo or non-treatment group. NA
- g. Definition of treatment failure or participant removal criteria. NA
- h. Description of what happens to participants receiving therapy when study ends or if a participant's participation in the study ends prematurely.
NA this is an observational trial.

5. Inclusion/Exclusion Criteria

a. Inclusion Criteria:

1. Has SCD, any genotype
2. Is being converted from full agonist opioid therapy to buprenorphine.
3. Able to provide consent
4. Is between the ages 18 and 100.

b. Exclusion Criteria:

1. Unwilling to sign consent.
2. Medical disorder, condition, or history that in the investigator's judgement would impair the patient's ability to participate or complete this study or render the patient to be inappropriate for enrollment.

6. Drugs/ Substances/ Devices

- a. The rationale for choosing the drug and dose or for choosing the device to be used.
NA
- b. Justification and safety information if FDA approved drugs will be administered for non-FDA approved indications or if doses or routes of administration or participant populations are changed. NA
- c. Justification and safety information if non-FDA approved drugs without an IND will be administered. NA

7. Study Statistics

- a. Primary outcome variable.
Primary Endpoint: This will be a descriptive study assessing the safety and benefit of converting subjects from full agonist opioids to buprenorphine. Data will be collected on need for hospitalization within 72 hours of conversion due to withdrawal induced VOC, as well as average COWS scores.
- b. Secondary outcome variables.
Secondary Endpoint: Measurement of quality of life and decreased pain measured by the BPI, ASCQ-Me, PROMIS Pain Interference, PROMIS Physical Function and decreased acute care utilization.
- c. Statistical plan including sample size justification and interim data analysis.
Descriptive study: Paired t-test will be used to compare patient's results on surveys and acute care utilization pre- and post- conversion.
- d. Early stopping rules.
NA

8. Risks

- a. Medical risks, listing all procedures, their major and minor risks and expected frequency.
- b. Participants may feel uncomfortable filling out surveys. Steps taken to minimize the risks.
Participants can stop filling out surveys at any time.
- c. Plan for reporting unanticipated problems or study deviations.
All study deviations and adverse events will be reported to the IRB.
- d. Legal risks such as the risks that would be associated with breach of confidentiality. NA

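### Does leaving the "pre" survey unnamed let recovery from withdrawal count as benefit in the paired t-test?

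*Combined protocol and SAP*

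**What the plan says.** The study procedures (part a, Study design) schedule ASCQ-Me, BPI, PROMIS Pain Interference and PROMIS Physical Function at these times:

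- **Item 1, up to 90 days before day 0, with consent:** "complete HRQoL tool (ASCQ-Me) (R),brief pain inventory (BPI) (R", plus the two PROMIS forms.
- **Item 3a, day 0:** "Subject will complete ASCQ-Me, PROMIS Pain Interference, PROMIS Physical Function, and BPI with 7 day anchor (R".
- **Item 5, follow-up:** days 14, 30, 90 and 180.

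The opening paragraph of the procedures says that the discussion before enrolment covers "the need to be in mild- moderate withdrawal prior to initiating buprenorphine", and that "most patients will be weaned down as much as possible from their current opioid dose prior to initiating the protocol below". On day 0, "Prior to discharge from SCIC subject will have COWS assessment, pain rating collected" (item 3b). Part c adds: "The initial visit is part of routine care that we provide for conversion from opioids to buprenorphine".

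Section 7c gives the whole analysis: "Paired t-test will be used to compare patient's results on surveys and acute care utilization pre- and post- conversion". It names no baseline survey and no main follow-up visit. It states no significance level or sample size and calls the study descriptive. The surveys are secondary endpoints (section 7b). The primary endpoint (section 7a) is about safety: "Data will be collected on need for hospitalization within 72 hours of conversion due to withdrawal induced VOC", together with average COWS scores.

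**The concern.** A paired t-test needs one value before and one after. The schedule supplies two candidates for the first and four for the second, and the plan picks none.

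The two candidates for the first may not be equivalent. Day 0 appears to be the conversion visit, since COWS is recorded before the patient leaves and the initial visit is described as routine conversion care. If patients complete the surveys while in withdrawal, their scores may be worse than usual. A later return to their usual state would then appear as improvement, and there is no comparison group to show otherwise.

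These surveys are the main evidence on pain and quality of life, so a claim of benefit could rest partly on recovery from withdrawal. Leaving the baseline open also permits a choice after the data are seen.

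**Working it through.** **No stated figure to reproduce.** The documents give no sample size, significance level, standard deviation or effect size for the surveys.

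**Count of possible comparisons.** 2 candidate baselines × 4 follow-up visits = 8 pairs per instrument. With four instruments counted as one score each, that is 8 × 4 = 32. The plan does not reduce this number.

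**Illustration of the possible bias.** All inputs are assumptions:

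- n = 15 or 20. This is borrowed from the group already converted in routine care, the only patient count in the documents. It is not the prospective sample size.
- Two-sided 5% test.
- Correlation ρ between before and after scores: 0.5, varied from 0.3 to 0.7.
- No true benefit, and a temporary day 0 worsening of d score SDs that has gone by follow-up.

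The SD of the paired difference is √(2(1−ρ)) score SDs. The t statistic therefore has noncentrality δ = d√n / √(2(1−ρ)), and the chance of a false improvement is P(T > t₀.₉₇₅), with T noncentral t on n−1 degrees of freedom. The critical values are 2.145 (n = 15) and 2.093 (n = 20). At ρ = 0.5 the divisor is 1. For d = 0.2, δ = 0.2 × √15 = 0.775 or 0.2 × √20 = 0.894.

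| d (score SDs) | ρ | n = 15 | n = 20 |
|---|---|---|---|
| 0 | any | 0.025 | 0.025 |
| 0.1 | 0.5 | 0.055 | 0.062 |
| 0.2 | 0.5 | 0.108 | 0.133 |
| 0.3 | 0.5 | 0.190 | 0.246 |
| 0.5 | 0.5 | 0.438 | 0.564 |
| 0.2 | 0.3 | 0.089 | 0.107 |
| 0.2 | 0.7 | 0.152 | 0.194 |

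If a 1 SD worsening affects only one day of a 7-day recall, and scores average evenly over days, then d = 1/7 ≈ 0.14 and the rate is 7% to 9%. If pain were eased at day 0, the same rates would apply to false worsening.

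**Do the documents support a shift of known sign or size?**

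- *Order of survey and first dose.* Not stated in the available text, part of which was removed before the procedures.
- *COWS on day 0.* It is taken before discharge, so it need not describe the patient when the survey was completed.
- *72-hour hospitalization endpoint.* Its window reads most naturally as following conversion, so it says little about the days a day 0 survey recalls.
- *Direction.* The Background (section 3) says that opioid-induced hyperalgesia may contribute to chronic pain. Weaned patients could therefore report less pain at day 0, which would reverse the bias.

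**Would the consent survey be a better baseline?**

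- It may be up to 90 days old, and no minimum gap from day 0 is set.
- Weaning is placed before the listed protocol, whose item 1 is the consent survey. On a plain reading, both surveys follow the wean.
- If it carried half of a 0.5 SD shift (d = 0.25, ρ = 0.5), the false-improvement rate would still be 0.145 (n = 15) or 0.185 (n = 20).
- If its age lowered ρ from 0.5 to 0.3, power for a true 0.5 SD gain would fall from 0.438 to 0.332 (n = 15) or from 0.564 to 0.434 (n = 20).

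**The case for a change.** The strongest case for a change is that section 7c is where the baseline belongs and it is not there. Calling the study descriptive does not excuse this, because the section specifies an inferential test. Naming one baseline and one main follow-up visit would cost a sentence, require no new visit or survey, and close off a choice made after seeing the results. The arithmetic is correct, and even a modest day 0 dip would push the false-improvement rate well above 2.5%.

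Much of this stands. The definition is missing, a day 0 dip is plausible, and an explicit statement would be tidier.

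Two parts do not stand. First, a dip is not inseparable from benefit: the same instruments are completed at consent and on day 0, so the change between them can be inspected, to the extent that the consent survey predates the dip. Second, the documents do not establish the consent survey as the right baseline. Patients have already decided to convert before enrolling. If they decide when symptoms are bad, that survey is itself open to regression to the mean. For patients already enrolled, a baseline named now would not be fully in advance either.

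**Conclusion.** No change to the plan follows. Section 7c leaves a definition unwritten; it does not state a rule that can be shown to give a wrong answer. Analysts must choose a baseline to run the test at all. With both surveys in hand, they can sensibly report results against each and show the change from consent to day 0. Which survey should lead is a fair trade-off: day 0 is closer to conversion but may reflect withdrawal, while the consent survey is older, may also follow the wean, and may leave residual bias with less power.

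The illustrated false-improvement rates at ρ = 0.5, from about 6% for a 0.1 SD dip to 44% to 56% for a 0.5 SD dip, rest entirely on an assumed shift, correlation, sample size and significance level. They show how the mechanism would work, not what will happen in this study. The question reaches only the secondary survey endpoints. Hospitalization within 72 hours and COWS do not use the surveys, and neither does acute care utilization, which has its own windows (6 months before enrolment, 3 years after conversion).

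This conclusion would change if the study documents fixed day 0 as the sole baseline and showed that the survey is completed during withdrawal.

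### From day 181 to year 3, acute care utilization rests on EPIC and CRISP with no end-of-observation date or person-time, so months after a death (or an uncaptured move) add zero visits and can look like benefit

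*Combined protocol and SAP*

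**What the plan says.** In the study procedures, part a, item 6 sets the long-term source and windows: "Data will be extracted from EPIC and CRISP on health care utilization for the 6 months prior to enrollment and 3 years post conversion". Item 5 adds another source at the survey contacts: "Acute care utilization will be collected from subject, medical record and Crisp". Those contacts fall on "day 14, day 30, day 90, and day 180", in person, by phone or online, and none is scheduled later. Part c nevertheless gives a three-year horizon: "Each participant will be enrolled for 3 years and will have up to 6 study visits".

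Section 7b makes "decreased acute care utilization" part of the secondary endpoint. Section 7c names a paired t-test of values before and after conversion and gives no rule for scaling, censoring or missing data.

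Two form headings where such a rule might have appeared are answered as not applicable. Part g reads "Definition of treatment failure or participant removal criteria. NA". Part h, on premature end of participation, reads "NA this is an observational trial".

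**The concern.** An extract of encounters shows visits that took place. Without a date on which observation ended, it cannot tell a patient who is well from one who has died or is being treated elsewhere. Because fewer visits count as benefit, a month in which the patient could not have been seen enters the analysis in the same form as a good month.

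Some deaths over three years are foreseeable. The Background says of sickle cell disease: "The disease reduces life expectancy by approximately 30 years compared to the general population". That sentence gives no three-year death rate, so it shows relevance and not size. At stake is whether a reported fall in utilization reflects less acute care or less observed time.

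**Working it through.** The plan states no sample size, visit rate or loss rate, so there is no figure of its own to reproduce. The following is an illustration.

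**Inputs from the document.** Pre window 6 months and post window 36 months (item 6). Last contact day 180, about month 6 (item 5). Time resting on records only: 36 − 6 = 30 months.

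**Assumptions.** 20 patients; equal visit rates, unchanged by conversion; all visits captured up to the loss and none after it; post-conversion counts divided by a fixed 36 months. The prospective number is not stated. Twenty is the upper end of the 15-20 already converted patients in item 7, a group for whom item 7 does not itself specify three-year extraction.

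**1. One patient lost at month t.** Apparent fall = 1 − t/36.
- t = 6: 30/36 = 83%
- t = 12: 24/36 = 67%
- t = 18: 50%
- t = 24: 33%

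**2. Cohort with k patients lost at month t.** Apparent fall = k(36 − t)/(20 × 36).

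| k | t = 6 | t = 12 |
|---|---|---|
| 1 | 30/720 = 4.2% | 24/720 = 3.3% |
| 2 | 60/720 = 8.3% | 48/720 = 6.7% |
| 3 | 90/720 = 12.5% | 72/720 = 10.0% |

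**3. Losses spread over time.** Let a share f be lost by month 36 at constant hazard h = −ln(1 − f)/36. The observed share of time is (1 − e^(−36h))/(36h). For f = 5%, 10%, 20% and 30% the spurious fall is 2.5%, 5.1%, 10.4% and 15.9%. If losses occur only in months 6 to 36, uniformly, the mean exit is month 21 and the fall is f × 15/36: 2.1%, 4.2%, 8.3% and 12.5%.

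**4. Effect on the paired t-test.** Simulation: 4,000 replicates, two-sided 5% level, constant-hazard losses from conversion, no true change. Visits are gamma-Poisson with shape 1.5 and a mean of 3 or 6 per 6 months. The table gives the chance of a significant false benefit with the fixed 36-month divisor.

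| Lost by month 36 | 20 patients | 50 patients |
|---|---|---|
| 0% | about 2% | about 2% |
| 10% | about 4% | 6-9% |
| 20% | 7-9% | 15-24% |
| 30% | 12-18% | 30-47% |

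**5. Dependence on scaling.** Take a patient with an unchanged rate who dies at month 7.
- Raw counts, 36 months against 6: the ratio is 7/6, an apparent rise of 17%. With full follow-up it would be 36/6 = 6, so the unseen time still lowers the figure but no fall appears.
- Six months on each side: the post window is complete and there is no bias.
- Fixed 36-month divisor: 1 − 7/36, an apparent fall of 81%.

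**6. Observed person-time.** Expected visits are proportional to t and the divisor is t, so the ratio is 1 and the expected fall is 0% for any f. In the simulation the false-benefit chance stayed at 2-3%.

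**The case against.** A reader might infer several stronger claims that the documents do not support.

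- *All three years come from records alone.* Item 5 also takes utilization from the participant through day 180. The gap starts on day 181.
- *The plan scores a patient who dies as a success.* No such rule is stated. Zero visits after death is the default result of following the text, and visits before death still count.
- *The problem is independent of the unequal windows.* It is not. As step 5 shows, its visible effect depends on how 3 years are set against 6 months, which the plan leaves open.
- *The bias always favors benefit.* Unseen time after conversion does act that way, but care missed in the 6-month pre window, for example in a recent arrival, acts in the opposite direction.
- *Moving away has the same effect as death.* The coverage of EPIC and CRISP is not defined, so this part is conditional.

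It is also fair to say that part g asks about treatment failure and removal, so its answer is weak evidence about observation time. Adverse events go to the IRB (section 8c), so deaths the team learns of may be recorded, although nothing links them to the utilization analysis. The case report forms and a portion of the text before the study procedures were not available, so a rule there cannot be excluded. The study calls itself descriptive, and the effect is modest when few patients are lost.

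These points narrow the claim and lower its weight. None supplies an end-of-observation date or a person-time rule.

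**Conclusion.** The point holds in limited form. After day 180 the only named sources are EPIC and CRISP, and no available text asks when each patient stopped being observable or relates counts to observed time. Unseen months after conversion therefore pull the post-conversion figure down, in the direction the endpoint counts as benefit.

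Under the stated assumptions, one to three losses among 20 patients produce a spurious cohort fall of roughly 3% to 13%. It would be larger if heavy users are the ones lost. The cohort size, the losses and the 36-month divisor are not in the plan.

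Only a secondary endpoint is affected. The primary safety outcome, admission in the first 72 hours and COWS scores, is not. The change should be made before the utilization analysis because it is cheap and the error would be hard to see in the results.

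**What to change.** Amend item 6 and section 7c as follows.

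1. At the utilization extraction, record for each patient the date of death or of known departure from the area or from care.
2. Otherwise, treat the patient as observed to the end of the window if later evidence exists from routine, non-acute sources such as clinic visits, refills or contact. Do not end time at the last acute encounter: that ties person-time to the outcome and cuts off well patients early. Where neither kind of evidence exists, list the patient as lost and show the result with time ended at the last routine evidence and with the full window.
3. Analyze utilization before and after conversion as rates per observed person-time. This also settles the 6-month against 3-year mismatch.
4. Report deaths and losses beside the utilization result, since a rate while alive does not itself register a death.
5. Show any analysis limited to patients observed for the whole window only as a sensitivity analysis, noting that it excludes those who died.

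The cost is one extra date per patient from charts already being opened, a few sentences of text, and slightly less person-time. Rates from very short follow-up will be unstable, so observed time should be tabulated with them.
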